5.7 Diet/Activity/Other Considerations

5.7.1 Diet

Subjects should maintain a normal diet unless modifications are required to manage an AE such as diarrhea, nausea or vomiting.

5.7.2 Contraception

Pembrolizumab, vorinostat, and temozolomide may have adverse effects on a fetus in utero. Furthermore, it is not known if pembrolizumab, temozolomide and vorinostat have transient adverse effects on the composition of sperm.

For this trial, male subjects will be considered to be of non-reproductive potential if they have azoospermia (whether due to having had a vasectomy or due to an underlying medical condition).

Female subjects will be considered of non-reproductive potential if they are either:

(1) postmenopausal (defined as at least 12 months with no menses without an alternative medical cause; in women < 45 years of age a high follicle stimulating hormone (FSH) level in the postmenopausal range may be used to confirm a post-menopausal state in women not using hormonal contraception or hormonal replacement therapy. In the absence of 12 months of amenorrhea, a single FSH measurement is insufficient.);

OR

(2) have had a hysterectomy and/or bilateral oophorectomy, bilateral salpingectomy or bilateral tubal ligation/occlusion, at least 6 weeks prior to screening;

OR

(3) has a congenital or acquired condition that prevents childbearing.

Female and male subjects of reproductive potential must agree to avoid becoming pregnant or impregnating a partner, respectively, while receiving study drug and for 120 days after the last dose of study drug by complying with one of the following:

(1) practice abstinence[†] from heterosexual activity;

OR

(2) use (or have their partner use) acceptable contraception during heterosexual activity.

Acceptable methods of contraception are[‡]:

Single method (one of the following is acceptable):

- intrauterine device (IUD)
- vasectomy of a female subject's male partner
- contraceptive rod implanted into the skin

Combination method (requires use of two of the following):

- diaphragm with spermicide (cannot be used in conjunction with cervical cap/spermicide)
- cervical cap with spermicide (nulliparous women only)
- contraceptive sponge (nulliparous women only)
- male condom or female condom (cannot be used together)
- hormonal contraceptive: oral contraceptive pill (estrogen/progestin pill or progestinonly pill), contraceptive skin patch, vaginal contraceptive ring, or subcutaneous contraceptive injection

†Abstinence (relative to heterosexual activity) can be used as the sole method of contraception if it is consistently employed as the subject's preferred and usual lifestyle and if considered acceptable by local regulatory agencies and ERCs/IRBs. Periodic abstinence (e.g., calendar, ovulation, sympto-thermal, post-ovulation methods, etc.) and withdrawal are not acceptable methods of contraception.

‡If a contraceptive method listed above is restricted by local regulations/guidelines, then it does not qualify as an acceptable method of contraception for subjects participating at sites in this country/region.

Subjects should be informed that taking the study medication may involve unknown risks to the fetus (unborn baby) if pregnancy were to occur during the study. In order to participate in the study subjects of childbearing potential must adhere to the contraception requirement (described above) from the day of study medication initiation (or 14 days prior to the initiation of study medication for oral contraception) throughout the study period up to 120 days after the last dose of trial therapy. If there is any question that a subject of childbearing potential will not reliably comply with the requirements for contraception, that subject should not be entered into the study.

5.7.3 Use in Pregnancy

If a subject inadvertently becomes pregnant while on treatment with study regimen, the subject will immediately be removed from the study. The site will contact the subject at least monthly and document the subject's status until the pregnancy has been completed or terminated. The outcome of the pregnancy will be reported to the Sponsor Sponsor (Moffitt Cancer Center) and to Merck without delay and within 24 hours to the Sponsor and within 2 working days to Merck if the outcome is a serious adverse experience (e.g., death, abortion, congenital anomaly, or other disabling or life-threatening complication to the mother or newborn).

The study investigator will make every effort to obtain permission to follow the outcome of the pregnancy and report the condition of the fetus or newborn to the Sponsor. If a male subject impregnates his female partner the study personnel at the site must be informed immediately and the pregnancy reported to the Sponsor and to Merck and followed as described above and in Section 7.2.2.

5.7.4 Use in Nursing Women

It is unknown whether study drugs are excreted in human milk. Since many drugs are excreted in human milk, and because of the potential for serious adverse reactions in the nursing infant, subjects who are breast-feeding are not eligible for enrollment.

5.8 Subject Withdrawal/Discontinuation Criteria

Subjects may withdraw consent at any time for any reason or be dropped from the trial at the discretion of the investigator should any untoward effect occur. In addition, a subject may be withdrawn by the investigator or the Sponsor (Moffitt Cancer Center) if enrollment into the trial is inappropriate, the trial plan is violated, or for administrative and/or other safety reasons. Specific details regarding discontinuation or withdrawal are provided in Section 7.1.4 – Other Procedures.

A subject must be discontinued from the trial for any of the following reasons:

• The subject or legal representative (such as a parent or legal guardian) withdraws consent.

- Unacceptable adverse experiences as described in Section 5.3.2
- Confirmed radiographic disease progression

Note: For unconfirmed radiographic disease progression, please see Section 7.1.2.6

Note: A subject may be granted an exception to continue on treatment with confirmed radiographic progression if clinically stable or clinically improved, please see Section 7.1.2.6

- Unacceptable adverse experiences as described in Section 5.3.2
- Intercurrent illness that prevents further administration of treatment
- Investigator's decision to withdraw the subject
- The subject has a confirmed positive serum pregnancy test
- Noncompliance with trial treatment or procedure requirements
- The subject is lost to follow-up
- Completed 15 months of uninterrupted treatment with pembrolizumab or 20 administrations of study medication, whichever is later.

Note: 15 months of study medication is calculated from the date of first dose.

Administrative reasons

The End of Treatment and Follow-up visit procedures are listed in Section 6 (Protocol Flow Chart) and Section 7.1.5 (Visit Requirements). After the end of treatment, each subject will be followed for 30 days for adverse event monitoring (serious adverse events will be collected for 90 days after the end of treatment as described in Section 7.2.3.1). Subjects who discontinue for reasons other than progressive disease will have post-treatment follow-up for disease status until disease progression, initiating a non-study cancer treatment, withdrawing consent or becoming lost to follow-up. After documented disease progression each subject will be followed by telephone for overall survival until death, withdrawal of consent, or the end of the study, whichever occurs first.

5.9 Subject Replacement Strategy

In dose escalation phase, subject will be replaced if they are considered inevaluable. A subjects will be considered DLT-evaluable if they have incurred a DLT within a DLT evaluation period or meet all of the following criteria: a) have received at least 85% of the prescribed doses of vorinostat, b) have received at least 85% of the prescribed doses of pembrolizumab, and c) have received the full dose (60 Gy) of radiation.

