5.3 Trial Treatments

Treatment must begin within 21 days of registering to the trial. Treatment should also begin ≥ 3 weeks and ≤ 6 (+/1) weeks following surgery. Each cycle will consist of 12 weeks.

Dose Escalation Cohort:

Treatment will include two phases: 1) concurrent radiotherapy phase and 2) maintenance phase. Dose escalation will occur separately for concurrent radiotherapy part of treatment and maintenance part of treatment.

The dose of pembrolizumab will be 200 mg dose IV every 3 weeks. The starting dose (i.e., dose level 1) of vorinostat was 200 mg/day orally on days 1-5 every week during radiotherapy and 300 mg/day orally 1 week on 1 week off during maintenance phase, starting after completion of concurrent therapy with radiation (+/- 3 days). The dose of vorinostat during radiotherapy was reduced to 100 mg mg/day orally on days 1-5 every week due to DLT. This dose is well tolerated and is currently being expanded.

The starting dose of vorinostat during maintenance phase, beginning after completion of concurrent therapy with radiation (+/- 3 days) was 300 mg/day orally 1 week on 1 week off. The dose is escalated to 400 mg/day orally 1 week on 1 week off, as per schema in a 3+3 fashion.

Concurrent Radiotherapy Phase:

During concurrent radiotherapy phase of treatment, patients with newly diagnosed GBM will receive radiotherapy (60 Gy in 30 daily fractions) as mentioned above.

Temozolomide (75 mg/m²/day orally) will be administered daily during the course of radiotherapy as per standard of care [22]. Temozolomide will be administered continuously from Day 1 of radiotherapy to the last day of radiation at a daily oral dose of 75 mg/m2. The dose will be determined using actual body surface area (BSA) as calculated in square meters at the beginning of the concomitant treatment. The BSA will be calculated from the height obtained at the screening visit and the weight obtained at the visit immediately before the first day of treatment. The dose of temozolomide does not have to be adjusted unless there has been at least a 10% change in body weight; recalculation of dose for < 10% weight changes is allowed at the discretion of the Investigator. The daily dose will be rounded to the nearest 5 mg.

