A dose-limiting toxicity (DLT) will be defined as any one of the following adverse events occurring within 6 weeks from last dose of radiation therapy for radiotherapy phase and 4 weeks from the start day of maintenance dose of vorinostat [Cycle 1 Day 43 (+/-3)] for maintenance phase:

CNS toxicities:

Acute CNS toxicities (occurring \leq 30 days after completing radiation therapy):

 Any grade 3 or higher central nervous adverse events including but not limited to headache, dizziness, vertigo, new onset seizures, cerebral edema, cerebral hemorrhage, and new onset neurologic deficit.

Delayed onset CNS toxicities (occurring >30 days after completing radiation therapy):

• Any grade 3 or 4 adverse event arising within the irradiated volume including but not limited to focal neurological deficits.

Non-CNS toxicities:

- Any Grade 4 immune-related adverse event (irAE)
- Any \geq Grade 3 colitis
- Any Grade 3 or 4 non-infectious pneumonitis irrespective of duration
- Any Grade 2 pneumonitis that does not resolve to ≤ Grade 1 within 3 days of the initiation of maximal supportive care
- Any Grade 3 irAE, excluding colitis or pneumonitis, that does not downgrade to Grade 2 within 3 days after onset of the event despite optimal medical management including systemic corticosteroids or does not downgrade to ≤ Grade 1 or baseline within 14 days
- Liver transaminase elevation > 8 × upper limit of normal (ULN) or total bilirubin > 5 × ULN
- Any \geq Grade 3 non-irAE, except for the exclusions listed below

The definition excludes the following conditions:

- Grade 3 fatigue lasting ≤ 7 days
- Grade 3 endocrine disorder (thyroid, pituitary, and/or adrenal insufficiency) that is managed with or without systemic corticosteroid therapy and/or hormone replacement therapy and the subject is asymptomatic
- Grade 3 inflammatory reaction attributed to a local antitumor response (eg, inflammatory reaction)
- Concurrent vitiligo or alopecia of any AE grade

- Grade 3 infusion-related reaction (first occurrence and in the absence of steroid prophylaxis) that resolves within 6 hours with appropriate clinical management
- Grade 3 or 4 neutropenia that is not associated with fever or systemic infection that improves by at least 1 grade within 14 days. Grade 3 or Grade 4 febrile neutropenia will be a DLT regardless of duration or reversibility
- Grade 3 or 4 lymphopenia

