- Grade 3 or 4 thrombocytopenia that is not associated with clinically significant bleeding that requires medical intervention, and improves by at least 1 grade within 14 days
- Isolated Grade 3 electrolyte abnormalities that are not associated with clinical signs or symptoms and are reversed with appropriate maximal medical intervention within 3 days
- Immune-related AEs are defined as AEs of an immune nature (ie, inflammatory) in the absence of a clear alternative etiology. In the absence of a clinically significant abnormality, repeat laboratory testing will be conducted to confirm significant laboratory findings prior to designation as a DLT. Laboratory abnormalities that are not deemed to be clinical significant will not be considered a DLT.

While the rules for adjudicating DLTs in the context of dose exploration are specified above, an AE not listed above may be defined as a DLT after a consultation with the sponsor and investigators, based on the emerging safety profile.

Dose escalation will be determined based on the occurrence of DLTs. For the purposes of determining whether to advance the dose levels, DLTs will be counted by patient. For all observed toxicities, subjects should be assessed for inter-current illness or other causes and treated as appropriate.

In the event of the development of any grade 3 or 4 toxicity felt to be at least possibly related to pembrolizumab, pembrolizumab will be held until resolution to grade 1 or baseline assuming that occurs within 6 weeks window. Treatment with pembrolizumab can be resumed after resolution of DLT to grade 1 or baseline except for following adverse events: Grade 4 infusion reactions, \geq Grade 3 pneumonitis, \geq Grade 3 nephritis, \geq Grade 3 colitis, increased alanine aminotransferase (ALT) or aspartate aminotransferase (AST) greater than 5 times upper limit of normal or total bilirubin greater than 3 times upper limit of normal.

Dose escalation for vorinostat will follow the standard 3+3 design. The enrollment to expansion cohort for radiotherapy phase will be delayed for 6 weeks after the completion of radiation therapy by the last patient enrolled at the MTD dose level for radiation therapy phase. The enrollment to expansion cohort for maintenance phase will be delayed for 4 weeks after the start day of maintenance dose of vorinostat [Cycle 1 Day 43 (+/-3)] by the

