5.3.2.2.2 Vorinostat

Dose interruption/hold/modification for vorinostat can occur at any time during treatment on study and are only performed if the event that caused the modification is possibly, probably or definitely related to vorinostat. Dosing interruptions are permitted in the case of medical / surgical events or logistical reasons not related to study therapy (e.g., elective surgery, unrelated medical events, patient vacation, and/or holidays).

Toxicity	Actions
Grade 1 hematological ANC ≥1500 Platelets < 100,000 but >75,000	1. Continue with protocol therapy.
Grade 2 hematological Platelets < 75,000 but > 50,000 Neutrophils (ANC) < 1500 but > 1000	 Hold vorinostat until toxicity recovered to ≤ grade 1 Check CBC prior to next planned vorinostat dose If recovered resume treatment with no dose modification. If not recovered, continue to hold and re-check CBC at next planned vorinostat dose.
Grade 3-4 hematological Platelets and ANC Only Platelets < 50.0 x 10 ⁹ /L Neutrophils (ANC) < 1.0 x 10 ⁹ /L or Grade 3 non-hematological	 Interrupt vorinostat, instituting symptomatic therapy as appropriate, until recovery to grade ≤1 Reintroduce vorinostat as follows: reduce by one dose level. If vorinostat is already at the lowest dose level, discontinue further vorinostat. If toxicity remains at grade ≤1 after 4 weeks of treatment at reduced dosage, then at the discretion of the investigator a return to the initial vorinostat dosage may be made
- If reappearance of above after actions 1 & 2	Discontinue treatment with vorinostat
- If reappearance of above after actions 1-3	Repeat 1 & 2 above but not 3.
Grade 3 non-hematological (only) - If failure to return to grade ≤ 1 after action 1 Grade 4 non- hematological toxicity	Consider action 2 at the discretion of the investigator only if toxicity is grade 2, manageable, and patient was benefiting from therapy Discontinue vorinostat

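### Section 5.9 replaces DLT-free escalation patients who fall short on dosing, with no exception when study-drug toxicity caused the shortfall

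*Combined protocol and SAP*

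**What the plan says.** Section 5.9 states that in dose escalation a "subject will be replaced if they are considered inevaluable". A patient is evaluable if a DLT occurred in the evaluation period, whatever the exposure. Otherwise the patient must "a) have received at least 85% of the prescribed doses of vorinostat, b) have received at least 85% of the prescribed doses of pembrolizumab", and criterion c) adds the full 60 Gy. The reason for a shortfall plays no part. Neither *prescribed* nor the period over which the 85% is measured is defined.

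Section 5.3.1 says "Dose escalation will be determined based on the occurrence of DLTs", counted by patient. The DLT list has no item for doses held, missed or stopped because of toxicity. Its exclusions include "Grade 3 or 4 thrombocytopenia that is not associated with clinically significant bleeding that requires medical intervention", if it improves by at least one grade within 14 days, and neutropenia on similar terms.

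Section 5.3.2.2.2 tells the investigator, for grade 2 cytopenia, to "Hold vorinostat until toxicity recovered to" grade 1 or lower. For grade 3-4 cytopenia, vorinostat is interrupted until recovery and then the instruction is to "reduce by one dose level. If vorinostat is already at the lowest dose level, discontinue further vorinostat". Table 4 in Section 5.3.2.2.1 holds pembrolizumab for several grade 2 events, among them colitis, liver test elevation, hypophysitis and nephritis.

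**The concern.** The primary objective is safety, tolerability and the MTD. A patient who cannot take the regimen because of the study drugs is informative about tolerability. Section 5.9 treats that patient in the same way as one who misses doses for a logistical reason.

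The plan's own rules can produce such patients. Grade 2 cytopenia is on no DLT list but stops vorinostat until recovery. Uncomplicated, improving grade 3-4 neutropenia or thrombocytopenia is excluded as a DLT, yet it interrupts vorinostat and then reduces or ends it. In the radiotherapy phase, the dose now being expanded (100 mg/day, Level -1) is the lowest level in the table, so there the rule is discontinuation.

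In a 3+3 cohort one patient can decide the next step. The text should therefore settle whether such a patient is replaced, counted as DLT-free or counted against the dose. It does not.

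**Working it through.** **1. The plan's own figure.** Section 8.1 gives a maximum of 12 escalation patients: 2 levels × 6 = 12, and 12 + 20 = 32 in total. This reproduces, and it contains no allowance for replacements.

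**2. What happens to one patient.** Take a DLT-free patient whose vorinostat is held for grade 2 cytopenia.
- If *prescribed* means scheduled, held doses stay in the denominator. Below 85% the patient is replaced.
- If it means as modified, held doses leave the denominator. The patient stays and counts as DLT-free, possibly after a dose reduction.
- On both readings the cytopenia enters the Dose Escalation Decision Rule table only if the consultation clause in 5.3.1 is used to name it a DLT.

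**3. When a shortfall crosses 85% (scheduled reading).** Doses come from the schedules in 5.3 and the flow chart.
- Vorinostat, radiotherapy course only: 5 × 6 = 30 doses. One held 5-day week: 25/30 = 83%, fails. Four missed doses: 26/30 = 87%, passes. If radiotherapy takes 7 weeks, as 5.2.1 allows, 30/35 = 86%, passes.
- Vorinostat, full radiotherapy-phase DLT period (to 6 weeks after the last fraction): maintenance dosing from Day 43, one week on and one week off, adds about 21 doses (Days 43-49, 57-63, 71-77), so 30 + 21 = 51. One held 5-day week: 46/51 = 90%, passes. Eight missed doses: 43/51 = 84%, fails.
- Vorinostat, maintenance period, "4 weeks from the start day of maintenance dose of vorinostat": 14 doses. Three missed: 11/14 = 79%, fails. Two missed: 12/14 = 86%, passes.
- Pembrolizumab: one omitted infusion gives 1/2 = 50%, 2/3 = 67% or 3/4 = 75%, depending on the window. All fail. A delayed infusion that is still given need not.

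**4. Illustration only.** The documents give no rates. Assume a DLT probability p = 0.10, and a probability q of toxicity-related under-dosing without a DLT. A level is cleared with 0 DLTs in 3 patients, or 1 in 3 and then 0 in 3: P = (1−r)³ + 3r(1−r)⁵. Here r = p/(1−q) if such patients are replaced, r = p if they are kept as DLT-free, and r = p + q if all are counted against the dose. The table's trigger for grade 2 CNS toxicities is ignored.

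| q | Replaced | Kept as DLT-free | All counted |
|---|---|---|---|
| 0.10 | 0.89 | 0.91 | 0.71 |
| 0.20 | 0.86 | 0.91 | 0.49 |
| 0.30 | 0.83 | 0.91 | 0.31 |

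The chance that filling six evaluable places removes at least one such patient is 1 − (1−q)⁶ = 47%, 74% and 88%.

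**5. A related contradiction.** Section 5.3.1 does not count a first grade 3 infusion reaction resolving within 6 hours as a DLT. Its list of events after which pembrolizumab may not be resumed names only grade 4 infusion reactions. Table 4 (5.3.2.2.1) and Table 5 (5.6.1) end pembrolizumab for grades 3 and 4 alike.

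**The case against.** Much of the plan works against the problem.
- Any event that meets a DLT criterion counts whatever the exposure, and most related non-haematological events of grade 3 or higher do.
- Section 5.3.1 lets the sponsor and investigators name an unlisted event as a DLT, which can reach a grade 2 cytopenia or colitis.
- The decision table enlarges a cohort for two or more grade 2 CNS toxicities.
- Section 5.10 allows termination on the incidence or severity of adverse reactions, and the monitoring committee reviews adverse events monthly.
- For grade 2 cytopenia the count is rechecked before the next planned dose, so a hold may be short.
- The radiotherapy dose has already been reduced because of DLT, so that phase did respond to toxicity.

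These points limit the concern but do not remove it. The consultation clause is optional and not tied to missed doses. The CNS trigger covers one class of event. Termination and committee review do not say how a non-completer enters the 3+3 count. The reduction to 100 mg/day shows that DLTs were acted on; it says nothing about toxicity that falls outside the DLT list. Maintenance escalation is described as under way ("The dose is escalated to 400 mg/day orally 1 week on 1 week off, as per schema in a 3+3 fashion"), so the rule can still affect a decision.

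A reader might infer that any held vorinostat week, or any pembrolizumab hold, makes a patient inevaluable. The documents do not support that: 25/30 is only one possible denominator, and an infusion may be delayed rather than omitted.

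**Conclusion.** The point holds as a defect in a stated rule. Followed as written, Section 5.9 can take patients with toxicity-related shortfalls out of the count that sets the MTD, or leave them in as DLT-free, and the text does not say which. This depends on the toxicity not meeting a DLT criterion and on the consultation clause not being used.

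The size is unknown. A reader might take 86% against 49% at q = 0.20 as the error. It is not: both rates are assumed, and 49% requires every such patient, including one with a recovered grade 2 cytopenia, to count against the dose. Nor does the text show that the rule is simply too lenient. Replacement is stricter than keeping these patients as DLT-free (86% against 91%) and more lenient than counting them all. A reader might also infer that the MTD has already been distorted, but no replacement is reported anywhere in the documents.

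The conflict over pembrolizumab after a grade 3 infusion reaction is separate and does not depend on these assumptions.

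**What to change.** In Section 5.9:
- Limit replacement under all three criteria (vorinostat, pembrolizumab and 60 Gy) to reasons unrelated to study-drug toxicity.
- Keep each toxicity-related non-completer, and require an explicit, recorded decision through the consultation already provided in 5.3.1 before the cohort decision, so that none is replaced or silently counted as DLT-free.
- Define *prescribed doses* (scheduled or as modified, and how reduced doses count) and the 85% window for each phase.
- List any patients already replaced, with reasons.

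Separately, the sponsor must reconcile 5.3.1, Table 4 and Table 5 on pembrolizumab after a grade 3 infusion reaction. The choice of clinical rule is the sponsor's.

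The cost is a text amendment, one listing and a consultation per affected patient. The MTD decision may become somewhat more conservative, depending on the adjudications. If a fraction f of these patients is judged to have a DLT, the rate becomes p + fq, which exceeds the present p/(1−q) once f is above p/(1−q). At the assumed p = 0.10 and q = 0.20 that is 0.10/0.80 = 0.125, or one in eight. Below that fraction the rule would be slightly more permissive than now, which is why a bar on replacement without adjudication would not be enough.
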